## 1.0 TRIAL SUMMARY

Abbreviated Title	Pembrolizumab for PD-L1 gene-altered, relapsed/refractory DLBCL
Trial Phase	II
Clinical Indication	PD-L1 gene-altered relapsed/refractory diffuse large B cell lymphoma (DLBCL)
Trial Type	Interventional, single-arm, biomarker-driven
Type of control	Historical (DLBCL patients enrolled on KEYNOTE-013 study)
Route of administration	Intravenous
Trial Blinding	Unblinded Open-label
Treatment Groups	1
Number of trial participants	13-29
Estimated enrollment period	2 years
Estimated duration of trial	3-4 years
Duration of Participation	
Each subject will participate in the trial from the time he or she signs the Informed Consent Form (ICF) through the final protocol-specified contact.
 
After the initial pre-screening and screening phases, eligible subjects will receive pembrolizumab treatment at a dose of 200 mg IV every 3 weeks (Q3W) for a duration of 2 years (35 cycles). Treatment with pembrolizumab will continue until documented disease progression, unacceptable adverse event(s), intercurrent illness that prevents further administration of treatment, investigator's decision to withdraw the subject, subject withdraws consent, pregnancy of the subject, noncompliance with trial treatment or procedure requirements, or administrative reasons requiring cessation of treatment. After the end of treatment, each subject will be followed for the occurrence of adverse events and spontaneously reported pregnancy as described under section 7.2 of the protocol. Subjects who discontinue for reasons other than disease progression will have post-treatment follow-up for disease status until disease progression, initiating a non-study cancer treatment, withdrawing consent, or becoming lost to follow-up. All subjects will be followed by telephone for overall survival until death, withdrawal of consent, or the end of the study.

Estimated average length of treatment per patient	1 year

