Patients enrolled on this study will undergo serial peripheral blood samples for correlative analyses, and archived FFPE specimens will be collected and stored for future exploratory research. Disease response to pembrolizumab will be determined using the LYRIC response criteria (1), and will be performed at designated timepoints outlined in the Trial Flow Chart in Section 6.0, and any time disease progression is clinically suspected. Specific procedures to be performed during the trial, as well as their prescribed times and associated visit windows, are outlined in the Trial Flow Chart – Section 6.0. Details of each procedure are provided in Section 7.0 – trial procedures. After 24 months, ongoing disease re-assessments will be performed at the discretion of the treating physician. Any patient who experiences disease progression at any time will be removed from study, and alternative treatment can be pursued at the discretion of the treating physician. After the end of treatment, each subject will be followed for the occurrence of adverse events and spontaneously reported pregnancy as described in Section 7.2 of the protocol. Subjects who discontinue treatment for reasons other than disease progression will undergo post-treatment follow-up for disease status until disease progression, initiation of a non-study cancer treatment, withdrawal of consent, or becoming lost to follow-up. All subjects will be followed by telephone contact for overall survival until death, withdrawal of consent, or the end of the study, whichever comes first.

Adverse events associated with pembrolizumab often represent immune-related toxicities. These adverse events may occur shortly after the first dose or several months after the last dose of treatment. Pembrolizumab must be held for drug-related toxicities and severe or life-threatening

adverse events as per Table 3. See Section 5.2 for supportive care guidelines including use of corticosteroids.

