#### **5.5.2 Prohibited Concomitant Medications**

Participants are prohibited from receiving the following therapies during the screening and treatment phase of this trial:

- Anti-neoplastic biological therapy
- Immunotherapy not specified in this protocol
- Chemotherapy
- Investigational agents other than pembrolizumab
- Radiation therapy

- Note: Radiation therapy to a symptomatic solitary lesion may be allowed at the investigator's discretion, provided that study treatment is initiated at least 7 days after completion of all palliative radiation..
- Live vaccines within 30 days prior to the first dose of study treatment and while participating in the study. Examples of live vaccines include, but are not limited to, the following: measles, mumps, rubella, varicella/zoster, yellow fever, rabies, BCG, and typhoid vaccine. Seasonal influenza vaccines for injection are generally killed virus vaccines and are allowed; however, intranasal influenza vaccines (eg, FluMist®) are live attenuated vaccines and are not allowed.
- Systemic glucocorticoids for any purpose other than to modulate symptoms from an immune-related adverse event, or the use of palliative glucocorticoids during the screening phase of the study (steroids however must be discontinued within 7 days of the first dose of pembrolizumab treatment). The use of physiologic doses of corticosteroids may be approved after consultation with the sponsor.

Participants who, in the assessment by the investigator, require the use of any of the aforementioned treatments for clinical management should be removed from the study. All treatments that the investigator considers necessary for a participant's welfare may be administered at the discretion of the investigator in keeping with the standards of medical care.

Medications or vaccinations specifically prohibited in the exclusion criteria are not allowed during the ongoing study. If there is a clinical indication for any medication or vaccination specifically prohibited during the study, discontinuation from study therapy or vaccination may be required. The final decision on any supportive therapy or vaccination rests with the investigator and/or the participant's primary physician. However, the decision to continue the participant on study treatment requires the mutual agreement of the investigator, the Sponsor and the participant.

There are no prohibited therapies during the Post-Treatment Follow-up Phase.

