## **5.6 Participant Withdrawal/Discontinuation Criteria**

Participants may discontinue study treatment at any time for any reason, and may also be discontinued from study treatment at the discretion of the investigator should any untoward effect occur. In addition, a participant may be discontinued from study treatment by the investigator or sponsor if study treatment is inappropriate, the trial plan is violated, or for administrative and/or other safety reasons. Specific details regarding procedures to be performed at study treatment discontinuation are provided in Section 7.1.4 – Other Procedures.

A participant must be discontinued from study treatment but continue to be monitored in the study for any of the following reasons:

- The participant or participant's legally acceptable representative requests to discontinue study treatment
- Confirmed radiographic disease progression outlined in Section 7.1.2.6
- Any progression or recurrence of any malignancy, or any occurrence of another malignancy that requires active treatment
- Unacceptable adverse events as described in Section 5.2.2
- The participant has a medical condition or personal circumstance which, in the opinion of the investigator and/or sponsor, placed the participant at unnecessary risk from continued administration of study treatment.
- The participant has a confirmed positive serum pregnancy test
- Noncompliance with study treatment or procedure requirements
- Recurrent Grade 2 pneumonitis
- Discontinuation of treatment may be considered for participants who have attained a confirmed complete response (CR) and have been treated for at least 8 cycles (at least 24 weeks), receiving at least 2 doses of pembrolizumab beyond the date when the initial CR was declared. These participants may be eligible for second course treatment described in Section 5.2.3.
- The participant is lost to follow-up
- Completion of 35 treatments (approximately 2 years) with pembrolizumab

Note: The number of treatments is calculated starting with the first dose. Participants who stop the combination or pembrolizumab after receiving 35 doses may be eligible for retreatment if they progress after stopping study treatment provided they meet the requirements detailed in Section 5.2.3. Participants may be retreated in the Second Course Phase (Retreatment) for up to an additional 17 cycles (approximately 1 year).

- Administrative reasons

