##### **7.1.1.5.3 Subsequent Anti-Cancer Therapy Status**

The investigator or qualified designee will review all new anti-neoplastic therapy initiated after the last dose of trial treatment. If a participant initiates a new anti-cancer therapy within 30 days after the last dose of trial treatment, the 30 day Safety Follow-up visit must occur before the first dose of the new therapy. Once new anti-cancer therapy has been initiated, the participant will move into survival follow-up.

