##### **7.1.5.4.1 Survival Follow-up**

Participants who experience confirmed disease progression or start a new anti-cancer therapy, will move into the Survival Follow-Up Phase, and should be contacted by telephone every 12 weeks to assess for survival status until death, withdrawal of consent, or the end of the trial, whichever occurs first.

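### Section 5.5.2 removes patients who need a prohibited treatment from the study, in conflict with the follow-up sections; read literally, it would censor OS, and to a lesser degree PFS, in a way related to failure

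*Combined protocol and SAP*

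**What the plan says.** Section 5.5.2 of the protocol lists therapies prohibited during screening and treatment: anti-neoplastic biologics, other immunotherapy, chemotherapy, other investigational agents, radiation, live vaccines, and systemic glucocorticoids outside stated exceptions. Participants who, in the investigator's assessment, "require the use of any of the aforementioned treatments for clinical management should be removed from the study".

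The same section then speaks differently. Where a prohibited medication is indicated, "discontinuation from study therapy or vaccination may be required", and "the decision to continue the participant on study treatment requires the mutual agreement of the investigator, the Sponsor and the participant". It closes by saying that nothing is prohibited in post-treatment follow-up.

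Elsewhere:

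- Section 2.1: "All subjects will be followed by telephone contact for overall survival until death, withdrawal of consent, or the end of the study". The Trial Summary (Section 1.0) says the same.
- Section 5.6: "A participant must be discontinued from study treatment but continue to be monitored in the study for any of the following reasons". Need for a prohibited treatment is not itself on the list that follows.
- Section 7.1.1.5.3: "Once new anti-cancer therapy has been initiated, the participant will move into survival follow-up".
- Section 7.1.5.4.1: "Participants who experience confirmed disease progression or start a new anti-cancer therapy, will move into the Survival Follow-Up Phase", with telephone contact every 12 weeks.
- Sections 7.1.2.6.2 and 7.1.2.6.3: imaging ends at progression or at new anti-cancer treatment, among other stopping points.
- Section 8.2.3.1: PFS counts progression or death and OS counts death. The only censoring rule is for responders who go to stem cell transplant.

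**The concern.** Sections 1.0 and 2.1 give three ways out of survival follow-up: death, withdrawal of consent and end of study. Section 5.5.2, taken at its word, adds a fourth. A patient who needs chemotherapy, radiation or steroids while on treatment will often be one whose lymphoma is worsening.

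Such a patient need not yet have a documented event. Imaging is every 12 weeks, and an indeterminate response under LYRIC becomes progression only after repeat imaging within a further 12 weeks (Section 7.1.2.6.4). If a site closed follow-up in that window, the patient would be recorded as alive and event-free. Kaplan-Meier estimation would then treat that patient as having the same outlook as those still at risk, which is too favourable.

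OS and PFS are the secondary endpoints that Section 3.2 sets against KEYNOTE-013 Cohort 4D, in at most 29 patients. Follow-up that was never collected cannot be restored at analysis.

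**Working it through.** **1. Which endpoints depend on the reading**

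| Endpoint | Literal removal | Follow-up sections | Difference |
|---|---|---|---|
| ORR | missing outcome counts as non-response (8.1.1, 8.2.5.1) | same rule | none from censoring |
| OS | censored at removal | followed to death | all later deaths lost |
| PFS, anti-cancer treatment given | censored at removal | imaging ends at new therapy, death still counted | later deaths lost |
| PFS, other treatment (e.g. steroids, live vaccine) | censored at removal | imaging continues | later progressions and deaths lost |

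The full analysis set needs one dose and a baseline assessment (Section 8.2.4.1), so removed patients remain in it.

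**2. The plan's own figure**

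The plan gives no figure for this point. Its only design calculation is the Simon two-stage design (Section 8.1.3). The chance of success at response rate p is the sum over x = 3 to 13 of P(X1 = x) × P(X2 ≥ 8 − x), with X1 binomial(13, p) and X2 binomial(16, p). This gives 0.04999 at p = 0.15 and 0.907 at p = 0.40, with probability 0.692 of stopping early at p = 0.15. The stated design is reproduced and does not depend on the disputed sentence.

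**3. Illustration for OS and PFS**

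All inputs here are assumptions; the documents give none of them.

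- F, time to clinical failure: exponential, median 2 or 3 months.
- P, survival after failure: exponential, median 3 or 6 months. Death is at D = F + P.
- Share q removed at F without documented progression: 10% to 40%. Of 29 patients, 20% is 5.8 and 40% is 11.6.
- OS cut-off at 36 months; 400,000 simulated patients per scenario.

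OS under the follow-up sections uses D for everyone. Under literal removal, the share q is censored at F. Median OS in months:

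| Medians of F / P | 20%: follow-up → literal | Ratio | 40%: follow-up → literal | Difference |
|---|---|---|---|---|
| 2 / 3 | 6.0 → 6.4 | 1.07 | 6.0 → 7.0 | 1.0 |
| 2 / 6 | 9.2 → 9.5 | 1.03 | 9.1 → 10.1 | 1.0 |
| 3 / 3 | 7.3 → 7.9 | 1.08 | 7.3 → 8.7 | 1.4 |
| 3 / 6 | 10.6 → 11.2 | 1.06 | 10.6 → 12.1 | 1.5 |

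At 10% removed, the gain is 0.2 to 0.3 months.

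For PFS, the removed patients are assumed to start anti-cancer therapy, so imaging ends at F under either reading. Literal removal censors them at F; the follow-up sections count their death at D. Median PFS in months:

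| Medians of F / P | True | 20%: literal / later deaths counted | 40%: literal / later deaths counted |
|---|---|---|---|
| 2 / 3 | 2.0 | 2.5 / 2.5 | 3.3 / 3.3 |
| 2 / 6 | 2.0 | 2.5 / 2.7 | 3.3 / 3.7 |
| 3 / 3 | 3.0 | 3.8 / 3.7 | 5.0 / 4.5 |
| 3 / 6 | 3.0 | 3.8 / 3.9 | 5.0 / 5.2 |

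The two readings differ by at most 0.5 months, in either direction. Both overstate the true median, because imaging has stopped under both. The steroid case, where imaging would otherwise continue, is not modelled.

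**The case against.** The strongest reply is that the protocol does not use the phrase to mean loss of follow-up. Section 2.1 removes patients with progression from study and, in the same paragraph, follows all subjects for survival. Section 5.5.2 itself looks ahead to a post-treatment phase in which these therapies are allowed. Many affected patients would also meet a listed reason in Section 5.6, such as progression of any malignancy, a medical condition or noncompliance, and would then stay monitored. Section 2.1 calls for response assessment whenever progression is suspected, and Section 7.1.2.6.3 for imaging at discontinuation, so some events would be documented before any removal.

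This makes off treatment the probable intent and reduces the number of patients at risk. It does not remove the contradiction, because a site works from the sentence in front of it.

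A reader might infer more: that failing patients are dropped from PFS and OS, or that losing a share c of events lengthens both medians by 1/(1 − c), which is 1.25 at 20%. The documents do not support this.

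- Treated patients with a baseline assessment stay in the full analysis set; they are censored, not excluded.
- Not all are failing: live vaccines are on the list, and patients with documented progression already have their PFS event.
- The multiplier assumes that the event is lost at the moment it would occur. For OS, censoring comes before death, and the simulated ratio at 20% is 1.03-1.08.
- For PFS, an overstatement of that order (2.5 against 2.0 months) does appear, but nearly all of it remains under the other sections, since imaging ends at new anti-cancer therapy. That part belongs to the missing PFS rule for new therapy in Section 8.2.3.1, not to this sentence.

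**Conclusion.** The contradiction stands: Section 5.5.2 cannot be squared, as written, with Sections 1.0, 2.1, 5.6, 7.1.1.5.3 and 7.1.5.4.1, or with its own later text. Followed literally, it would censor patients early in a way related to failure. The main loss is OS. PFS loses later deaths, and also imaging in patients given treatments that are not anti-cancer.

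The effect is modest: median OS about 3-8% longer at 20% removed and 1.0-1.5 months longer at 40%, with a PFS difference between readings of at most 0.5 months and no consistent sign. These figures show direction and order of size only. They rest on assumed removal shares and exponential times, and they apply only if sites read the sentence literally.

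The primary ORR is protected by the non-response rule, provided that removed members of the full analysis set are not replaced under Section 5.7. The sample size is unaffected.

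**What to change.** Reconcile Section 5.5.2 with Sections 1.0, 2.1, 5.6, 7.1.1.5.3 and 7.1.5.4.1 by adding a statement that *removed* does not end study follow-up:

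- Survival contact continues for all subjects and ends only at death, withdrawal of consent or end of study.
- Disease imaging continues until progression or new anti-cancer therapy, on the schedule and with the other stopping points already in Sections 7.1.2.6.2, 7.1.2.6.3 and 7.1.5.4.

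Whether study treatment stops or continues in a given case is not a matter for this point. Section 5.5.2 is inconsistent on it, and the sponsor's reconciled clinical text must settle it.

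The cost is a sentence or two and cross-references. The calls and scans are already planned, and no patients or procedures are added. The change does not supply the missing PFS rule for new anti-cancer therapy in Section 8.2.3.1, which has to be written separately.

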### **5.5.3 Rescue Medications & Supportive Care**

Participants should receive appropriate supportive care measures as deemed necessary by the treating investigator. Suggested supportive care measures for the management of AEs with potential immunologic etiology are outlined along with the dose modification guidelines in Section 5.2.2, [Table 3]. Where appropriate, these guidelines include the use of oral or IV treatment with corticosteroids, as well as additional anti-inflammatory agents if symptoms do not improve with administration of corticosteroids. Note that several courses of steroid tapering may be necessary as symptoms may worsen when the steroid dose is decreased. For each disorder, attempts should be made to rule out other causes such as metastatic disease or bacterial or viral infection, which might require additional supportive care. The treatment guidelines are intended to be applied when the investigator determines the events to be related to pembrolizumab.

Note: If after the evaluation of the event, it is determined not to be related to pembrolizumab, the investigator does not need to follow the treatment guidance. Refer to [Table 3] in Section 5.2.2 for guidelines regarding dose modification and supportive care.

It may be necessary to perform conditional procedures such as bronchoscopy, endoscopy, or skin photography as part of evaluation of the event.

## **5.6 Participant Withdrawal/Discontinuation Criteria**

Participants may discontinue study treatment at any time for any reason, and may also be discontinued from study treatment at the discretion of the investigator should any untoward effect occur. In addition, a participant may be discontinued from study treatment by the investigator or sponsor if study treatment is inappropriate, the trial plan is violated, or for administrative and/or other safety reasons. Specific details regarding procedures to be performed at study treatment discontinuation are provided in Section 7.1.4 – Other Procedures.

A participant must be discontinued from study treatment but continue to be monitored in the study for any of the following reasons:

- The participant or participant's legally acceptable representative requests to discontinue study treatment
- Confirmed radiographic disease progression outlined in Section 7.1.2.6
- Any progression or recurrence of any malignancy, or any occurrence of another malignancy that requires active treatment
- Unacceptable adverse events as described in Section 5.2.2
- The participant has a medical condition or personal circumstance which, in the opinion of the investigator and/or sponsor, placed the participant at unnecessary risk from continued administration of study treatment.
- The participant has a confirmed positive serum pregnancy test
- Noncompliance with study treatment or procedure requirements
- Recurrent Grade 2 pneumonitis
- Discontinuation of treatment may be considered for participants who have attained a confirmed complete response (CR) and have been treated for at least 8 cycles (at least 24 weeks), receiving at least 2 doses of pembrolizumab beyond the date when the initial CR was declared. These participants may be eligible for second course treatment described in Section 5.2.3.
- The participant is lost to follow-up
- Completion of 35 treatments (approximately 2 years) with pembrolizumab

Note: The number of treatments is calculated starting with the first dose. Participants who stop the combination or pembrolizumab after receiving 35 doses may be eligible for retreatment if they progress after stopping study treatment provided they meet the requirements detailed in Section 5.2.3. Participants may be retreated in the Second Course Phase (Retreatment) for up to an additional 17 cycles (approximately 1 year).

- Administrative reasons

## **5.7 Participant Replacement Strategy**

Subjects may be replaced in the trial as needed to ensure that the required number of evaluable subjects is achieved for the designated statistical analyses as put forth in section 8.0.

## **5.8 Criteria for Early Trial Termination**

Early trial termination will be the result of the criteria specified below:

1. Quality or quantity of data recording is inaccurate or incomplete
2. Poor adherence to protocol and regulatory requirements
3. Incidence or severity of adverse drug reaction in this or other studies indicates a potential health hazard to participants
4. Plans to modify or discontinue the development of the study drug
5. The ORR does not meet stated hypothesis upon completion of the first phase of the study (< 3/13 responders)

In the event that Merck decides to no longer supply study drug, ample notification will be provided so that appropriate adjustments to participant treatment can be made.

[illegible]

Trial Period:	Screening Phase		Treatment Cycles a								End of Treatment	Post-Treatment		
Treatment Cycle/Title:	Pre-screening (Visit 1)	Main Study Screening (Visit 2)	1	2	3	4	To be repeated beyond 8 cycles				Discon	Safety Follow-up	Follow Up Visits	Survival Follow-Up
							5	6	7	8				
Scheduling Window (Days):	-28 to -11	-10 to -1		± 3	± 3	± 3	± 3	± 3	± 3	± 3	At time of Discon	30 days post discon	Every 12 weeks post discon	Every 12 weeks
LDH		X	X	X	X	X	X	X	X	X	X			
Urinalysis		X					X				X	X		
TSH		X			X		X				X	X		
Efficacy Measurements														
Tumor Imaging and bone marrow exam b		X b				X				X	X			
Tumor Biopsies/Archival Tissue Collection/Correlative Studies Blood														
PD-L1 FISH Assessment	X													
Archival or Newly Obtained Tissue Collection		X									X c			
Correlative Studies Blood Collection		X		X			X				X			
Baseline Stool Collection		X												

a For women of reproductive potential, a urine pregnancy test will be performed within 72 hours prior to the first dose of trial treatment. If urine pregnancy results cannot be confirmed as negative, a serum pregnancy test will be required (performed by the local study site laboratory).

bTumor imaging to consist of a PET scan and diagnostic CT scans of neck, chest, abdomen, and pelvis. Scans performed within 28 days of treatment allocation will be allowable. Bone marrow biopsy to also be performed at times of tumor imaging for patients with baseline involvement (this does not need to be performed for patients with clear progression on diagnostic imaging, and does not need to be repeated for patients with documented bone marrow clearance unless otherwise clinically indicated).

cA new biopsy will be performed whenever possible for patients developing progressive disease.

